3.4.2. Data Analysis

Primary Aim 1. In a randomized design, determine the efficacy of the 12-month ELM Intervention, relative to Education Control, in an ethnically diverse sample of MetS patients. We hypothesize that the ELM intervention will produce a clinically significant remission of the MetS in at least 40% of those treated, while the remission rate in the Enhanced Usual Care Arm will not be higher than 15% at 12 months.

For each arm, the proportion of patients in remission of MetS at 12 months will be computed. The appropriate 2-sample test (see 'Adjustment for Clustering' section) will be used to compare the proportions. We will also test the hypothesis that the intervention produces a 12-month MetS remission rate of $\geq 40\%$.

Identification of a clinically significant primary endpoint and threshold on that endpoint is crucial to the determination of whether or not a proposed treatment deserves further testing.¹⁰⁴ The dichotomous rate of MetS remission (i.e., no longer meeting criteria) is the most popular primary endpoint in clinical trials of the MetS.^{92-94, 105-107} A continuous MetS score has not been validated in American adults.^{108, 109}

Secondary Aim 2. To assess the sustainability of the combined ELM plus Extended Maintenance Intervention on remission of the MetS at 24 months. We hypothesize that the ELM intervention will produce a clinically significant remission of the MetS in at least 38% of those treated, while the remission rate in the Education Control arm will not be higher than 15%.

Analytic procedures will be exactly the same as those for the Primary Aim (above).

Secondary Aim 3. To assess the impact of the 12-month ELM Intervention, and the 24-month ELM plus Extended Maintenance Intervention, on intermediate behavioral outcomes (dietary intake, physical inactivity, and stress) and secondary outcomes (body mass index, vitality, and MetS components).

Separate analyses will be conducted for each outcome. Mean changes (from baseline to 12 or 24 months) between the two arms will be compared using the appropriate 2-sample test (see 'Adjustment for Clustering'). The dependent variable will be the respective outcome at 12 or 24 months and the covariate predictors will be the baseline value and treatment allocation.

Exploratory Aim 4. To develop a system for monitoring costs of the intervention and of medical care over 24 months of follow up in all randomized patients.

Cost and resource use information will be collected in all patients for the interventions (e.g., time cost for the interventions, productivity loss, enrollment in other wellness programs) and for their health care. Candidate program costs include fixed and variable costs of the ELM Intervention and Education Control. These costs

include the ELM Coach and Coach Assistant time spent delivering the program, time spent training and preparing for each group session and time spent making calls to patients between group sessions, valued at these positions' average hourly wage, group meeting costs (e.g., meeting room space, meals), printed materials, and pedometers. Candidate patient costs include the patient's time spent attending the group sessions, travel time between home and the group sessions, and productivity losses to due absenteeism and presenteeism (measured using the Work Productivity and Activity Impairment Questionnaire),¹³³ valued at the average wage adjusted for socio-demographic characteristics. Health care and wellness-related costs include the cost of primary care physician visits, emergency department visits, hospitalizations and other health and wellness provider visits.³⁴ In addition, the cost of participation in other wellness programs will be included, since ELM may be perceived as a substitute for other wellness programs that patients would otherwise engage in. Feasibility and accuracy of all data collected will be determined and a protocol for assessing costs will be developed.

Exploratory Aim 5. *To explore the impact of the ELM intervention at 12 and 24 months on selected biomarkers of CVD (hemoglobin A_{1c}, C-reactive protein, lipoprotein particle composition) and change in the social network.*

Analyses will be approached in the same way as the continuous variables outlined in Secondary Aim 3 above. Change in the social network will focus on: (1) network size; (2) frequency of contacts; and (3) overall social connectedness. We will consider use of analysis of variance with quintiles of social network summary scores¹⁴³ to identify network variables are related to MetS remission. In addition, we will specifically assess the number and frequency of contacts with other ELM participants.

Exploratory Aim 6. *To explore the acceptability of the intervention assessed as the screening to enrollment ratio, the dropout rate within each arm, and the perceived credibility of each arm.*

The DMC will keep records of screened, enrolled, and drop-out rates. Mean differences in credibility between the 2 arms will be assessed in the same way as the continuous variables outlined in Secondary Aim 3 above.

Exploratory Aim 7. *To explore the moderating effects of built and food environment on MetS remission in the ELM Intervention and Control arms at 12 and 24 months.*

[figure not shown]
Moderating effects will be tested using logistic regression analysis (see 'Adjustment for Clustering' section above) with the dependent variable of MetS remission and the covariates of treatment arm, moderator, and the treatment-by-moderator interaction term.

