3.4. Statistical analysis

3.4.1. Preliminary considerations

All statistical analyses will be performed using SAS v. 9.2. Basic summary statistics will be calculated for all outcome variables and covariates of interest. Continuous variables will be checked for normality using Q-Q plots.

3.4.1.1. Missing data. Analyses will use an intent-to-treat approach that includes all patients randomized. Study procedures have been proposed to minimize loss of data due to withdrawal or loss. However, sensitivity analyses will be employed to assess the impact of missingness and both conservative and liberal imputations will be used.

3.4.1.2. Adjustment for Clustering. Clusters exist within the intervention arm and analyses thus require consideration of the effects due to clustering, assessed by analyzing within- and between-cluster variance as well as estimating the intraclass correlation coefficient using generalized linear mixed effects modeling. The cluster effect will be deemed significant if the appropriate covariance parameter estimate obtained from the model has p -value <0.05 .¹⁴² In this event, rather than using a two-sample, two-sided, z-test to compare proportions between the two treatment arms and the t-test (or the Mann-Whitney test if distributions are sufficiently non-normal) for the comparison of means, the cluster-adjusted chi-square test will be used to compare proportions and the cluster-adjusted t-test (or the cluster-adjusted Wilcoxon Rank-Sum test if distributions are sufficiently non-normal) will be used to compare means. Similarly, rather than using linear regression analysis to analyze relationships between continuous dependent variables and indicated covariates, linear mixed modeling will be employed. Lastly, rather than using logistic regression analysis to assess relationships between dichotomous dependent variables and indicated covariates, generalized linear mixed effects modeling will be employed.

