3.4.3. Sample Size and Power

The **primary outcome** of the study is remission of MetS from baseline to the 12-month visit. We hypothesize that at least 40% of patients in the Intervention Arm, and no more than 15% in the control arm will achieve remission. This hypothesis is supported by the ELM proof-of-concept study and published data on 12- and 24-month MetS remission rates of 9-14% in both control groups' patients.^{93, 95, 106} The proposed study employs clusters within the treatment arm only. To estimate sample size, adjustments were made for the intra-class correlation coefficient (ICC). Using data from the ELM proof-of-concept study, we conservatively estimate the ICC to be

A two-sample, two-sided, z-test for proportions will be used to compare the rate of MetS remission between the two treatment arms with an overall significance level of 0.05.

The sample size chosen is 48 patients (16/arm). Required sample sizes were computed under several plausible scenarios, indicated by our proof-of-concept study and other relevant studies. Power was set at 80%, alpha was 0.05, and a 20% dropout rate was assumed. **Figure 5** shows that if a sample size of 48 is chosen, there will be adequate power to detect a statistical difference between a remission rate as low as 40% in ELM Intervention arm and as high as 15% in the Education Control arm. Similar sample sizes resulted when the number of participating sites, clusters per site, and patients per cluster (between 10 and 13) were varied. There will be inadequate power to detect an effect if the ELM Intervention effect erodes to below a 38% remission and the Education Control remission rate is as high as

15%. However, this state of affairs would suggest that more developmental work on either the treatment or control group is needed before progressing.

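### The 12- and 24-month remission comparisons use no baseline covariate; stratifying on baseline MetS component count is a cheap improvement that protects the estimate from chance imbalance

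*SAP*

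**What the plan says.** SAP 3.4.2, Primary Aim 1, compares the 12-month remission proportions as follows: "The appropriate 2-sample test (see 'Adjustment for Clustering' section) will be used to compare the proportions". Section 3.4.3 names the test: "A two-sample, two-sided, z-test for proportions will be used to compare the rate of MetS remission between the two treatment arms". If the ELM groups show a significant cluster effect, 3.4.1.2 replaces the z-test with a cluster-adjusted chi-square test, which also has no covariate. For 24 months, Secondary Aim 2 says "Analytic procedures will be exactly the same as those for the Primary Aim (above".

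The endpoint is described in 3.4.2 as "The dichotomous rate of MetS remission (i.e., no longer meeting criteria".

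Secondary Aim 3 covers "secondary outcomes (body mass index, vitality, and MetS components", analysed as change from baseline, so the components are measured at baseline. For those outcomes "the covariate predictors will be the baseline value and treatment allocation".

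Section 3.4.1.2 also provides logistic regression for dichotomous outcomes with covariates, or a generalized linear mixed model when clustering is significant. The only remission analysis that uses covariates is the moderator analysis of Exploratory Aim 7, and baseline severity is not among them.

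**The concern.** The endpoint is a threshold crossing. Someone who only just qualifies for MetS must lose one component to remit, and someone with more must lose several. Baseline component count should therefore predict remission, although the SAP does not say how strongly.

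The trial is small, so the arms can easily differ in baseline count by chance. An unstratified comparison carries that difference into the estimated treatment effect. The SAP treats the endpoint and its threshold as the basis for deciding whether the treatment merits further testing, so a few points matter. The data needed for adjustment are already collected.

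**Working it through.** **The plan's own figure.** Section 3.4.3 gives a total of 48 with 16 per arm, for 40% against 15%, two-sided alpha 0.05, 80% power and 20% dropout. With the pooled-variance formula,

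n per arm = [1.96·√(2·0.275·0.725) + 0.8416·√(0.40·0.60 + 0.15·0.85)]² / 0.25² = (1.238 + 0.510)² / 0.0625 = 48.9,

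so 49 evaluable per arm before dropout or clustering. The printed total is not reproduced, and two arms of 16 make 32. That is a separate matter, but it means the arm size here is an assumption: 24 (48/2), 48 (the total read as per arm) or a literal 16.

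**Other inputs.** From the SAP: 40% and 15% remission, two-sided 0.05. Assumed: simple 1:1 randomisation, half of patients at the lowest qualifying count, independent patients, and an odds ratio (OR) for remission, lowest count against more, of 1 to 6.

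**How often the arms are imbalanced.** The difference between arms in the number of lowest-count patients, plus n, is Binomial(2n, 0.5).
- 24 per arm: 15 points or more means at least 4 patients. Probability 0.312, or 0.156 in each direction. Mean imbalance in ELM's favour, given that it occurs: 0.222.
- 48 per arm: at least 8 patients. Probability 0.125, or 0.063 in each direction. Mean imbalance 0.201.

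**Effect on the raw difference.** Let a and b be ELM remission at the lowest and higher counts (average 0.40), and c and e the same for control (average 0.15). With mean imbalance δ,

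shift = (δ/2)·[(a − b) + (c − e)].

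| OR | a, b | c, e | Shift, 24/arm | Shift, 48/arm |
|---|---|---|---|---|
| 1.7 | 0.463, 0.337 | 0.183, 0.117 | 2.1 points | 1.9 points |
| 2.4 | 0.503, 0.297 | 0.204, 0.096 | 3.5 points | 3.1 points |
| 6 | 0.600, 0.200 | 0.248, 0.052 | 6.6 points | 6.0 points |

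For example, OR 6 at 24 per arm: 0.111 × (0.400 + 0.196) = 0.066. Simulation (200,000 trials per cell) agrees, with shifts of about 2.0 to 6.6 points at 24 per arm and 1.9 to 6.1 at 48. Imbalance against ELM gives the mirror image.

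**Stratified estimate.** The Mantel-Haenszel difference is Σ[(x₁n₀ − x₀n₁)/N] / Σ[n₁n₀/N] over the two strata. In the same imbalanced trials it is off by at most 0.2 points. The stratified test's type I error is about 4.9%.

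**All trials together.** Root mean square error at 24 per arm, in percentage points, raw to stratified: 12.38 to 12.53 (OR 1), 12.39 to 12.32 (OR 2.4), 12.38 to 11.74 (OR 6).

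**Power (%), planned z-test to stratified test.**

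| OR | 24/arm | 48/arm |
|---|---|---|
| 1 | 51.0 to 49.2 | 80.4 to 79.7 |
| 2.4 | 51.1 to 50.5 | 80.3 to 80.9 |
| 3 | 51.2 to 51.4 | 80.4 to 81.7 |
| 6 | 51.0 to 54.2 | 80.3 to 84.4 |

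At a literal 16 per arm: 38.4 to 34.1 (OR 1) and 38.2 to 38.2 (OR 6).

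**A second set of assumptions.** With three strata (shares 50/35/15%) and remission odds falling by a factor of 2, 3 or 5 per extra component, take trials at 24 per arm where ELM is worse by 0.3 or more in mean count. The raw difference averages 0.20, 0.18 and 0.16 against a truth of 0.25; the stratified one averages 0.25, 0.25 and 0.26.

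**The case against.** The strongest reply is that nothing here is wrong. A two-sample test of proportions is valid under randomisation and unbiased on average. That stands. A reader might infer that the SAP contradicts itself because Aim 3 adjusts for baseline and Aim 1 does not. It does not: the Aim 3 covariate is for continuous outcomes, and it shows only that the data exist and that baseline adjustment is already accepted.

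A second reply is that quoting only the imbalanced trials flatters the proposal. This also stands in part. The 31% counts both directions, only about 16% of trials favour ELM, and the error averaged over all trials barely moves unless the count predicts strongly. A reader might infer an assured gain in power; at 24 per arm the change is negative below an OR of about 3.

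A reader might also conclude that the fix should inflate the ELM-arm variance by a fixed intraclass correlation (ICC), because 3.4.1.2 adjusts only after a pretest ("The cluster effect will be deemed significant if the appropriate covariance parameter estimate obtained from the model has"). That is a different question. The planning ICC is not readable in the text at hand ("Using data from the ELM proof-of-concept study, we conservatively estimate the ICC to be" breaks off there). If the true ICC were 0, the stratified test with the ICC fixed at 0.02, 0.05 or 0.10 would have power of about 46%, 39% or 30% at 24 per arm, against about 51% for the plain z-test. Whether to replace the pretest should be decided separately.

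Finally, if randomisation was stratified by count, which the SAP does not show, there is less imbalance to remove.

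**Conclusion.** The point holds as a recommended improvement. Both remission comparisons leave out a baseline measure that, given how the endpoint is defined, should predict it. Stratifying removes a conditional error of about 2.0 to 6.6 points at 24 per arm, or 1.9 to 6.1 at 48 per arm, in the trials where chance imbalance reaches 15 points. Over all trials the gain is small, and power moves by about -2 to +3 points at 24 per arm and -0.8 to +4 at 48.

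These sizes depend on the assumed OR, the half share at the lowest count, simple randomisation, independent patients and the assumed arm size. They were worked at the 12-month rates; the 24-month ELM rate of 38% is close, but was not run separately. The documents do not support calling the planned test invalid or biased, and stratification repairs neither the sample size statement nor the clustering pretest.

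**What to change.** For Primary Aim 1 and Secondary Aim 2, prespecify a Mantel-Haenszel risk difference with its test and 95% confidence interval, stratified on baseline component count in two levels fixed in advance (lowest qualifying count against more). Report the raw proportions and the planned two-sample test alongside. Where 3.4.1.2 calls for cluster adjustment, put the same two-level count term into the generalized linear mixed model which that section already names for dichotomous outcomes with covariates; a plain Mantel-Haenszel test ignores the ELM groups. That model's effect is an odds ratio, so the raw proportions remain the risk-scale summary there. The single-arm test of ELM remission against 40% is unaffected.

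The cost is SAP wording and a little programming, with no new data. If count does not predict remission, about 1 to 2 points of power are lost at 24 to 48 per arm, and about 4 at 16 per arm. The benefit is smaller if randomisation was stratified by count.

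### The added one-sample test sets its threshold at the planned ELM remission rate (40%), so it almost always fails when ELM performs exactly as planned

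*SAP*

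**What the plan says.** Primary Aim 1 in SAP 3.4.2 states the hypothesis: "We hypothesize that the ELM intervention will produce a clinically significant remission of the MetS in at least 40% of those treated", with control remission no higher than 15% at 12 months. The analysis paragraph first plans a two-sample comparison of proportions and then adds: "We will also test the hypothesis that the intervention produces a 12-month MetS remission rate of" 40% or more. The next paragraph says that choosing an endpoint and a "threshold on that endpoint is crucial to the determination of whether or not a proposed treatment deserves further testing".

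SAP 3.4.3 uses the same rate for planning: "We hypothesize that at least 40% of patients in the Intervention Arm, and no more than 15% in the control arm will achieve remission". It claims that "there will be adequate power to detect a statistical difference between a remission rate as low as 40% in ELM Intervention arm" and one as high as 15% in control. The significance level there belongs to the two-sided z-test used to "compare the rate of MetS remission between the two treatment arms with an overall significance level of 0.05". The sample size is given as 48 patients and also as 16 per arm.

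SAP 3.4.1.2 says: "Clusters exist within the intervention arm and analyses thus require consideration of the effects due to clustering". The replacement tests it names are for two-arm comparisons and regression models.

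Secondary Aim 2 takes over the Primary Aim's procedures at 24 months, with a hypothesised ELM rate of at least 38%.

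**The concern.** The threshold of the single-arm test and the planning rate are the same number. To show that a rate reaches a threshold, a trial needs a true rate clearly above it. A trial planned on a true rate at the threshold has no more than the type I error rate as its chance of success, and recruiting more patients does not change that.

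The test is also not specified: the SAP gives no null, direction, alpha or one-sample method. It uses only the ELM arm, which is the clustered one, yet the cluster-adjusted tests named do not include a one-sample test.

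At stake is how the Primary Aim is reported. The paragraph that follows the test links a threshold to the decision on further testing. If ELM performs as planned, the report would probably show a won between-arm comparison (if the trial is large enough) beside a failed threshold test. That failure would say little about whether ELM reached 40%.

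**Working it through.** **Inputs from the SAP.** Threshold 40% (3.4.2, Primary Aim 1). Planning rates 40% v 15%, two-sided alpha 0.05 for the two-arm test (3.4.3). Sample size 48 patients, 16 per arm (3.4.3).

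**Assumptions.** Two arms of 16 make 32, not 48, so the ELM n is unclear. I take 16 (the stated arm size), 24 (half of 48) and 48 (if 48 is per arm). All ELM patients are analysed and clustering is ignored, because the ICC value is not legible in the text. The test is exact binomial, one-sided 0.025, with 0.05 as a check. The SAP states no power or size for this test, so there is no figure to reproduce.

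**Step 1: the general result.** With null p < 0.40, a level-alpha test must reject with probability at most alpha for every p below 0.40. The rejection probability is continuous in p, so it is also at most alpha at p = 0.40. This holds for any n, test statistic or ICC, provided the test is valid.

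**Step 2: cut-offs and power.** The cut-off r is the smallest r with P(X ≥ r | n, 0.40) ≤ 0.025. Power at p is P(X ≥ r | n, p).

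| ELM n | Cut-off | True 40% | True 50% | True 60% | True rate for 80% power |
|---|---|---|---|---|---|
| 16 | 11 (69%) | 1.9% | 10.5% | 33% | 75% |
| 24 | 15 (63%) | 2.2% | 15.4% | 49% | 68% |
| 48 | 27 (56%) | 1.7% | 23.5% | 75% | 61% |

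At one-sided 0.05 the cut-offs for 16 and 24 do not move. For 48 the cut-off becomes 26, with success of 3.3%, 33% and 83% at a true 40%, 50% and 60%. For 80% power at a true 50%, the smallest ELM n is 195 (cut-off 92) at one-sided 0.025, or 158 at one-sided 0.05.

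**Step 3: beside the two-arm test.** I enumerated all outcomes of both arms at 40% v 15%, with the pooled z-test, two-sided 0.05, in favour of ELM. The share of wins that fail is 1 − P(win both) / P(win two-arm).

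| Per arm | P(win two-arm) | P(win both) | Share of wins that fail the single-arm test |
|---|---|---|---|
| 16 | 0.3826 | 0.0188 | 1 − 0.0188/0.3826 = 95% |
| 24 | 0.5102 | 0.0216 | 1 − 0.0216/0.5102 = 96% |
| 48 | 0.8043 | 0.0166 | 1 − 0.0166/0.8043 = 98% |

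**Step 4: the opposite reading.** Suppose 40% or more is the null and non-rejection counts as support. At one-sided 0.025 the lower-tail rejection regions are at most 2/16, 4/24 and 12/48. A true rate of 30% is then not rejected with probability 90%, 89% and 72%. Such a test passes ELM easily at 40%, but it also passes a treatment well short of 40% most of the time.

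**The case against.** The strongest reply is that the SAP never says which hypothesis is the null. A hypothesis that includes equality is conventionally a null, and the talk of further testing and of more developmental work fits a futility-type screen. On that reading ELM at a true 40% is retained about 98% to 99% of the time. It stands that the failure in Steps 1 to 3 is conditional on 40% having to be demonstrated. It does not rescue the test, because Step 4 shows that the other reading discriminates poorly, and a plan that leaves the choice open has a defect in its own right.

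Second, 40% is worded as a floor, so the truth may be higher, and the 95% to 98% figures hold only at exactly 40%. That is correct. But power is still low at 50%, and no rate above 40% is planned on. The most favourable case computed at a true 60% is 83%, with 48 ELM patients and one-sided 0.05.

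Third, the test is introduced as an addition. It is not named as co-primary or as a gate, and the sentence on further testing mainly justifies the endpoint. This also stands, and it limits the harm to a misleading secondary result under the Primary Aim.

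Fourth, a 95% interval compared with 40% gives essentially the same inference as a one-sided 0.025 test. True; the gain is that an estimate with its uncertainty replaces a pass/fail result that would nearly always be a fail under the plan.

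**Conclusion.** The concern holds. If the single-arm test is meant to demonstrate a 12-month ELM remission rate of 40% or more, its chance of success at the planned 40% cannot exceed alpha: about 2% for 16, 24 or 48 ELM patients at one-sided 0.025. That core result rests only on the null being below 40% and the test being valid. It does not depend on the unclear sample size or on the ICC. The specific percentages assume an exact binomial test without clustering or dropout; a positive ICC would reduce the effective n and so the power above 40%. On the opposite reading the test is lenient rather than severe. Either way the result is uninformative or misleading, and the SAP does not specify the test well enough to say which applies. The wording of Secondary Aim 2 appears to carry the same problem to 24 months at 38%. The between-arm comparison is untouched, so this should be corrected but does not threaten the main efficacy test.

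**What to change.** In SAP 3.4.2, replace the single-arm test with the ELM remission rate and a 95% confidence interval that allows for clustering, shown beside descriptive benchmarks of 40% at 12 months and 38% at 24 months. State that the efficacy conclusion rests on the between-arm test. The threshold then stays visible for the decision on further testing. If a single-arm test is kept, set its null below the planning rate, justify that value, and state the alpha, the cluster method and the power.

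The change is to SAP wording only; no extra data or patients are needed. The cost is the loss of a formal single-arm test, and the interval will be wide. An observed rate near 40% gives an exact (Clopper-Pearson) 95% interval of 15% to 65% (6/16), 22% to 63% (10/24) or 26% to 55% (19/48), before any cluster adjustment. A retained test with a lower null would show only that the rate exceeds that null, not that it reaches 40%.

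### Secondary Aim 3, and Exploratory Aim 5 by cross-reference, state two analyses for each continuous outcome and do not say which gives the treatment effect

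*SAP*

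**What the plan says.** SAP section 3.4.2, Secondary Aim 3, has two consecutive sentences on how each continuous outcome is analysed. The first: "Mean changes (from baseline to 12 or 24 months) between the two arms will be compared using the appropriate 2-sample test", with a pointer to the clustering section. The second: "The dependent variable will be the respective outcome at 12 or 24 months and the covariate predictors will be the baseline value", together with the allocated arm.

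The pointer leads to SAP section 3.4.1.2, which keeps two families apart. Means are compared by a t-test, "or the Mann-Whitney test if distributions are sufficiently non-normal) for the comparison of means", or by cluster-adjusted versions of these if the cluster effect is significant. Covariate models come afterwards as a separate item: "rather than using linear regression analysis to analyze relationships between continuous dependent variables and indicated covariates, linear mixed modeling will be employed". Section 3.4.1 adds that "Continuous variables will be checked for normality using Q-Q plots".

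Two later aims refer back. Exploratory Aim 5 (CVD biomarkers and social network): "Analyses will be approached in the same way as the continuous variables outlined in Secondary Aim 3 above". Exploratory Aim 6: "Mean differences in credibility between the 2 arms will be assessed in the same way" as the Aim 3 continuous variables.

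**The concern.** A t-test or rank test of change takes no covariate, whereas the model in the next sentence adjusts for baseline. They are different analyses of the same outcome at the same visit, with different estimates, standard errors and p-values. No sentence makes one of them the main analysis or the other supportive.

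Two things are at stake. First, the reported result is not fixed in advance: where the two analyses fall on opposite sides of 0.05, the SAP does not settle which one is the finding. Second, if the test of change is the one used, precision is given up in a small trial although the more precise model is already written down.

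The scope is about 10 outcomes in Aim 3 (dietary intake, physical inactivity, stress, body mass index and vitality, plus five MetS components, where five is an assumption) and six in Aim 5 (three biomarkers and three network measures), each at two visits.

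**Working it through.** The SAP gives no power, standard deviation or effect size for these outcomes, so there is no figure of its own to reproduce. The conflict is one of wording; the arithmetic only shows how much the choice can matter.

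**Inputs**
- Baseline/follow-up correlation r: not in the SAP; assumed 0.3, 0.5, 0.7, 0.9.
- Patient variance 1 at baseline and follow-up, and independent patients: assumed.
- n = 24 per arm: an equal split of the 48 patients in section 3.4.3. This is an assumption, because the same sentence gives 16 per arm and 2 × 16 = 32. With the stated 20% dropout, 24 × 0.8 = 19.2, so about 19 per arm.

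**Step 1. Variance of the arm difference**

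Test of change: 2(1 − r)(2/n).

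Baseline-adjusted model: (1 − r²)(2/n)(1 + 1/(2n − 4)). The last factor is the expected cost of estimating the baseline slope; it is 1 + 1/44 = 1.023 at n = 24.

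The ratio, adjusted to change, is (1 + r)/2 × (1 + 1/(2n − 4)).

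| r | Change, n = 24 | Adjusted, n = 24 | Ratio | Variance cut | Standard error cut | Ratio, n = 19 |
|---|---|---|---|---|---|---|
| 0.3 | 0.1167 | 0.0776 | 0.665 | 34% | 18% | 0.669 |
| 0.5 | 0.0833 | 0.0639 | 0.767 | 23% | 12% | 0.772 |
| 0.7 | 0.0500 | 0.0435 | 0.869 | 13% | 7% | 0.875 |
| 0.9 | 0.0167 | 0.0162 | 0.972 | 3% | 1% | 0.978 |

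The choice of n hardly matters.

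**Step 2. Allowing for ELM groups**

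Add t/k to both variances, with an assumed between-group variance t = 0.05 and k = 2 groups. That is 12 per group, within the SAP's "patients per cluster (between 10 and 13) were varied". At r = 0.3: (0.0776 + 0.025)/(0.1167 + 0.025) = 0.724. The four ratios are 0.724, 0.821, 0.913 and 0.989, so the variance cut is 28%, 18%, 9% and 1%. Clustering shrinks the gain but does not reverse it.

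**Step 3. False positives if the choice is left open**

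Simulation with no treatment effect, 24 per arm, independent normal data, 20,000 trials per r and two-sided 0.05. The t-test on change was compared with the baseline-adjusted regression. The rate for either being significant equals half the sum of the two single rates and the disagreement rate.

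| r | Change test | Adjusted model | Disagree | Either significant |
|---|---|---|---|---|
| 0.3 | 5.1% | 4.9% | 5.5% | 7.7% |
| 0.5 | 4.9% | 4.9% | 4.4% | 7.1% |
| 0.7 | 4.8% | 4.9% | 3.5% | 6.6% |
| 0.9 | 4.6% | 4.8% | 2.0% | 5.7% |

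At r = 0.3, before rounding: (5.125 + 4.895 + 5.470)/2 = 7.745%. Each analysis alone holds close to 5%. Runs with 19, 38 and 48 per arm gave 6.0% to 7.9% for either.

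**The case against.** The best defence is that the second sentence merely specifies the comparison announced in the first. It follows directly, and the section pointed to also covers regression and mixed models. Part of this stands: once baseline is a covariate, the arm coefficient and its p-value are the same whether the dependent variable is the change or the follow-up value. The mention of change is therefore not in itself the conflict. What remains is the phrase naming a 2-sample test, which section 3.4.1.2 defines as tests without covariates and keeps apart from regression. Loose drafting is a plausible explanation, but it does not tell the analyst which result to report.

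The size is also open to challenge. The correlation is assumed, and at r = 0.9 the gain in precision is negligible, so a material loss is not shown for any named outcome. That stands.

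A reader might infer that the two analyses will often disagree on significance. In simulation with the adjusted model at about 79% power, they do so in 23%, 17%, 11% and 6% of trials across the four correlations. The SAP states no power for these outcomes, and under no effect the figures are about 5% down to 2%. The larger set is not an estimate for this trial.

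A reader might also count Aim 6 credibility as a third place with two analyses. The SAP speaks there of mean differences, not change, and mentions no baseline credibility value. Without one, neither a change score nor a baseline-adjusted model can be computed. The cross-reference may fit badly, but two competing analyses are not shown.

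Finally, naming the model leaves the choice between linear regression and mixed model to the cluster test at p < 0.05. That is true, but a written rule governs that choice.

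**Conclusion.** The point holds for Aim 3 and, by cross-reference, Aim 5: two analyses are stated and neither is designated as the source of the treatment effect. Naming either would remove the ambiguity; the baseline-adjusted model is preferable because it is the more precise and is already in the plan.

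Under the stated assumptions, the variance advantage runs from about 34% down to 3% (28% down to 1% with the assumed group variance). Choosing whichever analysis is significant would give about 6–8% false positives per outcome instead of 5%. Nothing in the SAP says that the choice would be made that way; the figure shows only what the wording leaves possible.

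The SAP does not support a claim of bias, since both analyses target the same mean difference under randomization, nor any effect on the primary remission comparison. This should be corrected, but its weight is moderate: only secondary and exploratory outcomes are affected.

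**What to change.** - **Aim 3:** state that the baseline-adjusted model (12- or 24-month value on arm and baseline, by linear regression or by the linear mixed model under the existing clustering provisions) is the single source of the estimate, interval and p-value for each continuous outcome with a baseline value, at each visit. Label the 2-sample test of change, including its rank version, as supportive.
- **Skewed outcomes:** if an outcome is expected to be skewed, name it and its transformation before outcome data are examined. For counts, such as network size, choose a transformation that is defined at zero. A general rule to transform whatever looks skewed would reopen a data-dependent choice.
- **Aim 5:** follows through its cross-reference.
- **Aim 6 credibility:** if no baseline value is collected, replace the cross-reference with a plain 2-sample comparison.

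The cost is a few sentences of wording and slightly more analysis work. The model, the baseline covariate and the clustering provisions are already in the plan, so no new data or visits are needed.
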